8.10. Concomitant Medications or Therapies

Approximately 30% of participants will be allowed to remain on no more than 2 preventive migraine medications (listed in protocol Appendix C), provided the medication is recognized to have at least moderate evidence of efficacy or is commonly used. Participants must have been on a stable, well-tolerated dose of this preventive medication for at least 2 months prior to screening (visit 1) and would be expected to remain on this medication for the duration of the trial. For the remaining approximately 70% of participants, these medications are not allowed for migraine or for any other indications.

Participants will be allowed to use acute medications to treat acute migraine attacks, as needed, with the exception of medications containing opioids and barbiturates.

All concomitant medications will be coded using the WHO dictionary of medical codes. The concomitant medication will include all medications taken after the 1st IMP administration.

The incidence of concomitant medications will be summarized using descriptive statistics by therapeutic class and preferred term for each treatment group. Participants are counted only once in each therapeutic class category, and only once in each preferred term category.

The subset of concomitant pain medication and medication or therapy for migraine/headache will be summarized by the following indication categories.

- Medication from Appendix C for migraine/headache
- Medication from Appendix C for other reason than Migraine/Headache
- Migraine/headache prevention medication not from Appendix C
- NSAIDs for migraine/headache
- NSAIDs for other reason than migraine/headache
- Triptan for migraine/headache
- Triptan for other reason than migraine/headache
- Ergot for migraine/headache
- Ergot for other reason than migraine/headache
- Medication used for symptoms during migraine attack other than pain
- Other

8.11. Columbia Suicide Severity Rating Scale (C-SSRS)

The C-SSRS, combined with the Investigator's clinical evaluation, will be used to assess whether the participant has suicidal ideation or behavior and its severity (Posner et al 2011). The C-SSRS will be completed by a qualified rater trained to administer the scale at the investigational center based on discussion with the participant/caregiver. Any participant who demonstrates suicidal ideation and/or any suicidal behavior at any point during the trial as per C-SSRS and Investigator's clinical evaluation, should be withdrawn from the trial and discontinued from trial treatment. In addition, if a participant endorses suicidal ideation or behaviour at any point during the trial (including during screening), the Investigator must explain to the participant/caregiver the need for follow-up with a mental health professional and make any necessary referrals. Data for participants with positive findings from the C-SSRS will be listed.

9. TOLERABILITY VARIABLES AND ANALYSIS

Injection site reactions will be recorded as adverse events according to the following severity assessment criteria:

- Assessment of injection site erythema, induration, and ecchymosis will be recorded according to measurements: 5 to \leq 50 mm (mild), $>$ 50 to \leq 100 mm (moderate), and $>$ 100 mm (severe).
- Injection site pain will be recorded using the 11-point numerical rating scale and will be mapped to mild, moderate, or severe, according to participant's self-report of pain intensity.
- Appropriate treatment may be provided if necessary, in which case it must be recorded as concomitant medication.

Tolerability will be assessed by the following:

- the number (%) of participants who fail to complete the trial (day 85, final assessment)
- the number (%) of participants who fail to complete the trial due to adverse events

Local tolerability findings will be listed and summarized descriptively.

10. PHARMACOKINETIC ANALYSIS

Pharmacokinetic plasma concentration results (test IMP) will be tabulated descriptively at each planned sampling time point by weight cutoff.

In addition, the most appropriate population pharmacokinetic model will be developed. This analysis will be reported separately, as appropriate.

11. PHARMACOKINETIC/PHARMACODYNAMIC ANALYSIS

The pharmacokinetic/pharmacodynamic relationship may be estimated by compartmental techniques. The pharmacokinetic parameters will be based on test IMP measurements. The pharmacodynamic measures will be the efficacy/safety responses.

The pharmacokinetic/pharmacodynamic relationship may be estimated using the most appropriate model after comparing different candidate models for their quality of fit. If performed, this analysis will be reported separately.

12. IMMUNOGENICITY ANALYSIS

The impact of ADAs on safety and efficacy will be analyzed if the number of ADA-positive participants allows. If performed, this analysis will be reported separately.

13. STATISTICAL SOFTWARE

All data listings, summaries, and statistical analyses will be generated using SAS® version 9.4 or later.

15. CHANGES TO ANALYSES SPECIFIED IN THE TRIAL PROTOCOL

The subgroup analysis of ‘participants receiving alternative preventive medications that belong to the same classes but are not listed in protocol Appendix C’ specified in the protocol will not be performed, as it is not required.

The subgroup analysis of ‘participants receiving 2 preventive medications from protocol Appendix C’ will not be performed, as it is not required.

Participants from site █ will be excluded from all analysis sets due to GCP non-compliance. The site has been terminated from continuous participation in the trial.

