3. ANALYSIS SETS

3.1. Intent-to-Treat Analysis Set

The intent-to-treat (ITT) analysis set will include all randomized participants.

In the ITT analysis set, treatment will be assigned based on the treatment to which participants were randomized, regardless of which treatment they actually received.

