3.2. Safety Analysis Set

The safety analysis set will include all randomized participants who receive at least 1 dose of IMP.

In the safety analysis set, treatment will be assigned based on the treatment participants actually received, regardless of the treatment to which they were randomized.

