3.3. Full Analysis Set

The full analysis set (FAS) will include all participants in the ITT population who receive at least 1 dose of IMP and have at least 10 days of diary entries postbaseline for efficacy assessments on the primary endpoint.

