5. TRIAL POPULATION

5.1. General

The ITT analysis set will be used for all trial population summaries unless otherwise specified. Summaries will be presented by treatment group and for all participants unless otherwise noted.

For continuous variables, descriptive statistics (n, mean, SD, SE, median, minimum, and maximum) will be provided. For categorical variables, participant counts and percentages will be provided. Categories for missing data will be presented if necessary.

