5.2. Participant Disposition

Participants screened, screening failures, and the reasons the participants were not randomized will be summarized only for the overall group using participant counts.

Participants randomized (ie, in the ITT set), participants randomized but not treated, participants in the safety analysis set, full analysis set and per-protocol analysis set, participants who complete the trial, and participants who withdraw from the trial will be summarized using descriptive statistics. Participants who withdraw from the trial will also be summarized using descriptive statistics by reason for withdrawal. The denominator for calculating the percentages will be the number of ITT population.

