5.5. Prior Therapy and Medication

Any prior therapy, medication, or procedure a participant has had before IMP administration will be recorded on the CRF. Trade name or INN, indication, and dosage will be recorded. The

sponsor will encode all therapy and medication according to the World Health Organization (WHO) drug dictionary (WHODrug).

The incidence of prior therapies and medications will be summarized using descriptive statistics by therapeutic class and PT. Participants are counted only once in each therapeutic class category, and only once in each PT category. Prior therapies and medications will include all medications taken and therapies administered before the 1st day of IMP administration.

The subset of prior medications will be summarized for the following categories.

- Medication from Appendix C for migraine/headache
- Medication from Appendix C for other reason than Migraine/Headache
- Migraine/headache prevention medication not from Appendix C
- NSAIDs for migraine/headache
- NSAIDs for other reason than migraine/headache
- Triptan for migraine/headache
- Triptan for other reason than migraine/headache
- Ergot for migraine/headache
- Ergot for other reason than migraine/headache
- Medication used for symptoms during migraine attack other than pain
- Other

5.6. *Electrocardiography*

Electrocardiogram findings by Investigator (normal, abnormal not clinically significant and abnormal clinically significant) and by Cardiologist (normal, abnormal) overall and at last visit will be summarized.

5.7. *Physical Examinations*

Physical examinations results will be listed. Participants with at least 1 abnormal finding (overall) and abnormal findings for each category will be summarized.

5.8. *Childbearing Potential and Methods of Contraception*

All participants must be of non-childbearing potential or be using highly effective contraception as defined in the protocol. Information related to childbearing potential will be collected and listed.

Methods of contraception will be collected and this data will be listed.

5.9. *Trial Protocol Violations*

Protocol deviations (PD) will be collected and reviewed by the trial team prior to database lock and will be provided in a data listing. Participants with at least 1 important protocol deviation will be summarized for each category using descriptive statistics.

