6.2.3. Sensitivity Analysis

6.2.3.1. MMRM Analysis

A mixed-effects repeated measures (MMRM) analysis model will be implemented to estimate the mean change from baseline in the monthly average number of migraine days for the overall 3 months treatment period and by each month to support the primary analysis.

Each participant's monthly number of migraine days *during the 4-week period* for month 1, month 2 and month 3 will be calculated by formula (2) in Section 6.1 based on the e-diary responses for that month. If a participant is early terminated or has intermittent missing days and has less than 10 days of e-diary entries for a month, that month's value will be considered as missing as described in Section 4.3.

The MMRM model will include baseline value, treatment, puberty status, sex, region, weight category (<45.0 kg or ≥ 45.0 kg), baseline preventive migraine medication use (yes/no), month and treatment-by-month interaction as fixed effects, and participant in the repeated statement as a random effect. The stratification factors (as randomized) will be used in the model. The unstructured covariance structure will be used for the repeated observations within a participant. If the model does not converge, then simpler covariance structures with fewer parameters will be used in the following order (stopping at the first converging structure); heterogeneous Toeplitz, Toeplitz, or compound symmetry with a robust sandwich estimator (Liang and Zeger, 1986). For a model based estimator of the covariance (ie, unstructured, heterogeneous Toeplitz, or Toeplitz) for making inferences between treatment groups, especially at a particular visit, the Kenward-Roger degrees of freedom will be employed (Kenward and Roger, 1997).

LS means for the treatment groups, LS means for the treatment differences (TEV48125-48125 - placebo), and corresponding 95% confidence intervals and associated p-values will be calculated by month and for the overall treatment period.

The LS means \pm SE of monthly change from baseline values estimated by MMRM will be plotted by month for each treatment group.

A supplementary analysis using the ITT population will also be carried out for the primary efficacy endpoint.

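### The SAP removes one site's participants from every analysis set but still defines ITT as all randomized and Safety as all dosed, so children dosed there would vanish from disposition counts and aggregate safety tables

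*SAP*

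**What the plan says.** SAP 15, which lists changes from the protocol's analyses, states that participants from one site (number redacted) "will be excluded from all analysis sets due to GCP non-compliance" and that the site has been terminated. The SAP amendment history records this addition under version 02, dated 20 December 2024. It records no matching edit to Section 3.

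The current set definitions carry no exception:

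- SAP 3.1: "The intent-to-treat (ITT) analysis set will include all randomized participants".
- SAP 3.2: "The safety analysis set will include all randomized participants who receive at least 1 dose of IMP".
- SAP 3.3: "The full analysis set (FAS) will include all participants in the ITT population who receive at least 1 dose of IMP", with a further requirement for diary data.

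Protocol 9.1.1 to 9.1.3 give the same definitions. The SAP Introduction says the SAP takes precedence over the protocol where they differ, with differences explained in the CSR.

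The sets then drive the outputs. SAP 5.1: "The ITT analysis set will be used for all trial population summaries unless otherwise specified". SAP 5.2 begins its list with "Participants randomized (ie, in the ITT set), participants randomized but not treated" and uses ITT as the percentage denominator. SAP 8.1 assigns all safety analyses to the safety population.

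**The concern.** Two current parts of the SAP give different answers to the question of who is in the ITT and Safety sets. The precedence rule in the Introduction settles SAP against protocol. It does not settle SAP 3 against SAP 15.

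If SAP 15 governs, as its later and more specific wording suggests, the set names no longer mean what they say: ITT is not all randomized and Safety is not all dosed. Poor conduct at a site can be a good reason to distrust its efficacy data. It does not undo the fact that a child was randomized or received an injection. A reader of the tables could not see how many participants were removed from each arm, or what happened in aggregate to those who were dosed. The SAP does not commit to by-arm counts or to a safety summary for the site.

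**Working it through.** **1. Following the text through, for any participant randomized or dosed at the site**

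| Output | Set used | Effect of SAP 15 |
|---|---|---|
| Disposition (SAP 5.2) | Randomized is equated with ITT; ITT is the denominator | Dropped from the randomized count itself |
| Trial population summaries (SAP 5.1), including important deviations (SAP 5.9) | ITT | Dropped, including from the summary of deviations |
| Exposure and adverse event tables (SAP 8.1, 8.2, 8.4) | Safety | Dropped |
| Primary analysis (SAP 6.1, 6.2.2) | FAS | Dropped |
| ITT supplementary analysis (SAP 6.2.3.1) | ITT | Dropped |

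On deviations, SAP 5.9 promises that "Participants with at least 1 important protocol deviation will be summarized for each category using descriptive statistics". Under the ITT default, that summary would omit the site removed for non-compliance. On efficacy, SAP 6.2.3.1 says "A supplementary analysis using the ITT population will also be carried out for the primary efficacy endpoint", but that analysis cannot bring the site back, because the site is outside ITT as well.

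Some outputs are not clearly affected. Screened and screen-failure counts and the PK tabulations name no set. The exploratory analyses are redacted. The SAP does not say whether the listings keep these participants. Expedited safety reporting is untouched.

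**2. The plan's own design figure**

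Inputs from SAP 2.4: difference 1.7 days, SD 4.92, 133 evaluable per arm, 4% discontinuation, 278 randomized (139 per arm). SAP 7 gives two-sided 0.05.

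- SE = 4.92 × √(2/133) = 0.603 days.
- Power = Φ(1.7/0.603 − 1.96) = 0.804 (0.802 with the noncentral t), which agrees with the stated minimum of 80%.
- 266/0.96 = 277.1, rounded up to 278, as stated.

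**3. Size of the reporting gap**

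The documents do not give the number randomized or dosed at the site, so the sizes here are assumptions. Protocol 4.1.1 plans about 85 centers, giving an average of 278/85 = 3.3. I also take 10 and 20, all split equally by arm and all dosed.

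| Assumed site size | Missing from active arm | Share of 139 |
|---|---|---|
| 3.3 | 1.6 | 1.2% |
| 10 | 5 | 3.6% |
| 20 | 10 | 7.2% |

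SAP 8.1 splits the active arm by dose, and SAP 8.4 splits adverse event tables by age group. The share missing from a single cell could therefore be larger than this, or zero.

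**4. Effect on the primary estimate**

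Shift from including the site ≈ (site share of 278) × (gap between the treatment difference at the site and elsewhere).

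| Site size | Gap 1.7 days | In SE | Gap 4.92 days | In SE |
|---|---|---|---|---|
| 3.3 | 0.02 | 0.03 | 0.06 | 0.10 |
| 10 | 0.06 | 0.10 | 0.18 | 0.29 |
| 20 | 0.12 | 0.20 | 0.35 | 0.59 |

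The 1.7-day gap means no treatment difference at the site and the planned difference elsewhere. The 4.92-day gap is a deliberate extreme: with 1.7 days elsewhere, the site would have to favor placebo by 4.92 − 1.7 = 3.2 days.

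**5. Effect on power**

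This assumes the site's participants come out of the 278 and are not made up elsewhere. Removing 4, 10 or 20 randomized participants leaves 262.2, 256.4 or 246.8 evaluable (266 minus 0.96 of each) and power of 79.9%, 79.0% or 77.5%.

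**The case against.** The strongest reply is that this is mostly drafting. SAP 3 repeats the protocol's definitions. SAP 15 then states a specific exception under a heading for changes, and the amendment history repeats it. Read together, they leave little doubt about who is analyzed. SAP 2.5.2 requires the SAP and its amendments to be approved before database lock and unblinding. Protocol 10.5 foresees closing a center that does not follow GCP, although it does not address exclusion of data. Protocol 9.9 says deviations from the statistical plan will be described with reasons. Individual cases may still be visible: SAP 8.5 promises a listing for any death, and the deviation, adverse event and laboratory listings do not themselves name a set. If the data are unreliable, putting them back into safety tables or an ANCOVA adds noise.

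Much of this stands. The intent is probably clear, the exclusion is disclosed, individual listings may survive, and the case for re-running the efficacy model is debatable. It does not answer the main point. Resolving the conflict in favor of SAP 15 is exactly what removes dosed participants from the aggregate safety tables and randomized participants from the randomized count. The promises to explain changes do not commit to by-arm counts or to safety data for the site. The SAP also already has a per-protocol set (SAP 3.4) for important deviations, with the primary and secondary analyses repeated on it (SAP 6.1). Removal from ITT and Safety goes well beyond that.

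**Conclusion.** The concern holds. SAP 15 and SAP 3.1 to 3.3 conflict in current text. Following SAP 15 leaves anyone randomized or dosed at the site out of the set-based disposition counts, the deviation summary and the aggregate safety tables.

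The size is unknown. For assumed sites of 3.3 to 20 participants, 1.2% to 7.2% of the active arm would be missing from the safety tables. Including the site would shift the primary estimate by 0.02 to 0.12 days under the moderate assumption and by at most 0.35 days under the extreme one, against an SE of 0.60 days. No effect on the primary result is shown.

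Confidence is high on the mismatch in the text. The practical consequence depends on someone having been randomized or dosed at the site, which the documents do not confirm, and on the nature of the non-compliance, which is not given. This should be corrected, mainly for complete disposition and safety reporting.

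**What to change.** 1. Reconcile SAP 3.1 to 3.3 with SAP 15 by stating, set by set, whether the site is excluded.
2. Report the numbers randomized and dosed at the site, by arm, in the disposition table.
3. Keep its dosed participants in the safety set. At minimum, give a separate table and listing of their exposure, adverse events and serious adverse events.
4. Optionally, run the primary ANCOVA once with the site included, footnoted as supportive.

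The note to file dated 29 May 2025 says the trial analysis was conducted. If so, these items belong in the CSR and item 4 must be labelled post hoc. If the site's data cannot be used for items 3 or 4, say so in SAP 15 or the CSR and still give the counts.

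The cost is a few sentences, by-arm counts, one table and listing, and at most one extra model run. The drawback is that data of doubtful quality would appear in safety or supportive outputs, so these need a clear footnote.

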APPENDIX A. E-DIARY QUESTIONNAIRE

	The following questions are referring to yesterday (00:00 - 23:59)
A1	Did you have a headache yesterday?
A2	Did your headache last for 2 hours or more yesterday?
A3	On a scale of 0-10, how painful was your headache yesterday?
A4	Was your headache pain worse on one side (left or right) of your head yesterday?
A5	Was your head pain throbbing, pounding, or beating like a drum yesterday?
A6	Was your headache worse by doing simple activities like walking, bending or going up the stairs yesterday?
A7	Did you have stomach ache, feel sick to your stomach or did you throw up yesterday?
A8	Did light bother you or did you want to be in a dark room yesterday?
A9	Did sounds bother you or did you want to be alone in a quiet room yesterday?

	The following questions are referring to the day before yesterday (00:00 - 23:59)
A10	Did you have a headache the day before yesterday?
A11	Did your headache last for 2 hours or more the day before yesterday?
A12	On a scale of 0-10, how painful was your headache the day before yesterday?
A13	Was your headache pain worse on one side (left or right) of your head the day before yesterday?
A14	Was your head pain throbbing, pounding, or beating like a drum the day before yesterday?
A15	Was your headache worse by doing simple activities like walking, bending or going up the stairs the day before yesterday?
A16	Did you have stomach ache, feel sick to your stomach or did you throw up the day before yesterday?
A17	Did light bother you or did you want to be in a dark room the day before yesterday?
A18	Did sounds bother you or did you want to be alone in a quiet room the day before yesterday?

	The following questions are referring to the time DURING/BEFORE your headache yesterday (00:00 - 23:59)
B1	Think about the time during your headache yesterday. Did you have trouble seeing normally or did you see spots, stars, wavy lines, or flashes?
B2	Think about the time before your headache started yesterday. Did you notice any of the usual signs that a headache is coming? This could include seeing spots, stars, wavy lines, or flashes, having trouble speaking, feeling dizzy or having tingling, numbness or weakness in your arms or legs.
B3	Did you take a nap or go to sleep earlier than usual because of your headache yesterday?
B4	Did you take any medicine for your headache yesterday?
B5	What medicine did you take?
B6	How many doses of this medicine did you take?

	The following questions are referring to the time DURING/BEFORE your headache on the day before yesterday (00:00 - 23:59)
B7	Think about the time during your headache the day before yesterday. Did you have trouble seeing normally or did you see spots, stars, wavy lines, or flashes?
B8	Think about the time before your headache started the day before yesterday. Did you notice any of the usual signs that a headache is coming? This could include seeing spots, stars, wavy lines, or flashes, having trouble speaking, feeling dizzy or having tingling, numbness or weakness in your arms or legs.
B9	Did you take a nap or go to sleep earlier than usual because of your headache the day before yesterday?
B10	Did you take any medicine for your headache the day before yesterday?
B11	What medicine did you take?
B12	How many doses of this medicine did you take?

	The following questions are referring to yesterday (00:00 - 23:59)
C0	Even if you did not have a headache, did you feel fine yesterday?
C1	Even if you did not have a headache, did you sleep well yesterday?
C2	Even if you did not have a headache, did you eat normally yesterday?
C3	Even if you did not have a headache, did you miss any school time yesterday?
C4	Even if you did not have a headache, did you avoid playing any sports yesterday?
C5	Even if you did not have a headache, did you avoid watching television or movies yesterday?
C6	Even if you did not have a headache, did you avoid playing video games yesterday?
C7	Even if you did not have a headache, did you avoid reading yesterday?
C8	Even if you did not have a headache, did you avoid any other activities yesterday because of how your headache makes you feel or because of concern that you might have a headache?

	The following questions are referring to the day before yesterday (00:00 - 23:59)
C9	Even if you did not have a headache, did you feel fine the day before yesterday?
C10	Even if you did not have a headache, did you sleep well the day before yesterday?
C11	Even if you did not have a headache, did you eat normally the day before yesterday?
C12	Even if you did not have a headache, did you miss any school time the day before yesterday?
C13	Even if you did not have a headache, did you avoid playing any sports the day before yesterday?
C14	Even if you did not have a headache, did you avoid watching television or movies the day before yesterday?
C15	Even if you did not have a headache, did you avoid playing video games the day before yesterday?
C16	Even if you did not have a headache, did you avoid reading the day before yesterday?
C17	Even if you did not have a headache, did you avoid any other activities the day before yesterday because of how your headache makes you feel or because of concern that you might have a headache?

